6.2.3. Sensitivity Analyses of Primary Efficacy Endpoint

Sensitivity analyses will be performed to evaluate the robustness of the primary analysis results. Analyses will be performed for the overall population based on the outcome of the primary analyses including all subjects in the mITT set.

6.2.3.1. Missing Data Analyses Based on Multiple Imputation

The following sensitivity analysis based on multiple imputation will be performed, as appropriate, using the same statistical approach as the one used in the primary analysis:

- Subjects with treatment discontinuation or study withdrawal assessed as potentially related to study drug or lack of efficacy will have missing data after the discontinuation or withdrawal imputed via a control-based imputation based on the sham control subjects. This will be based on the mITT set.
 - Subjects who discontinue the treatment or study due to reasons that are potentially related to study drug or lack of efficacy include
 - Subjects who discontinue due to ocular adverse event, adverse event related to treatment, or adverse event related to injection procedure
 - Subjects who withdraw consent due to lack of efficacy (specify field includes ‘Lack of efficacy’) or not otherwise specified as not related to efficacy (specify field includes “Not specified”)
- Subjects with a monotone missing data pattern due to treatment discontinuation or study withdrawal will have missing data after the last assessment explicitly imputed by multiple imputation using a tipping point analysis method assuming missing not at random (MNAR). This will be based on the mITT set.

Imputation for the non-monotone missing pattern (i.e., arbitrary missing pattern) will be performed prior to the multiple imputation for the monotone missing pattern (i.e., where a missing GA area measurement at a visit for a subject implies that GA area measurements at all subsequent visits for that subject are missing).

For the nonmonotone missing pattern, missing value(s) between two visits with measured GA area will be imputed using the monotone data MCMC method, which was first proposed by Li (1988) and Liu (1993) described the algorithm. Multiple imputation will then be carried out for monotone missing pattern.

The two imputation methods will be implemented in SAS using the three standard steps to generate inference from imputed data: imputation step, analysis step, and pooling step.

Details are illustrated with SAS codes in Section 1.2.2.

- The missing data are filled in 1000 times to generate 1000 complete datasets.
- The 1000 complete datasets are analyzed by using the same approach as for the analysis for the primary objective.
- The results from the 1000 complete datasets are combined for the inference.

Methods used in the imputation step are described below.

- Pattern Mixture Model Method (a copy-reference approach): The pattern mixture model method will be implemented.
 - Subjects with monotone missing data in the pooled sham arm will have missing data imputed based on the observed values in the pooled sham arm.
 - For the active treatment arms, subjects with monotone missing data who discontinued treatment or withdrew from the study due to reasons that are potentially related to study drug or lack of efficacy will have missing data imputed based on the pooled sham arm.
 - For the active treatment arms, subjects with monotone missing data who did not discontinue treatment or withdraw from the study due to reasons that are potentially related to study drug or lack of efficacy will have missing data imputed based on the observed values in the corresponding treatment arm.
- Tipping Point Analysis Method (a delta-adjusted approach): The tipping point analysis method will be implemented for each active treatment arm under the MNAR assumption by searching for a tipping point that reverses the conclusion regarding positive treatment effect. For the pooled sham arm, subjects will have missing data imputed based on the observed values in the pooled sham arm. For the active treatments, subjects with monotone missing data without treatment discontinuation or early withdrawal will have missing data imputed based on the observed values in the corresponding treatment arm. For the active treatment arms, subjects with monotone missing data due to treatment discontinuation or early withdrawal will have the missing data imputed based on the available values (observed values plus values imputed for non-monotone missing data) in the same treatment arm with a shift parameter added to the imputed values. Multiple imputation will be implemented on the differences between two consecutive visits, with the shift parameter allocated to

the missing data point(s) proportionally across timepoints. (e.g., For a shift parameter of 0.48 mm^2 at Month 12, incremental shifts of 0.08 mm^2 would apply to Month 2, Month 4, ... and Month 12, respectively. $0.08 \text{ mm}^2 \times 6 \text{ visits} = 0.48 \text{ mm}^2$) The range of the shift parameters will be from 0.06 mm^2 to 0.72 mm^2 by increments of 0.06 mm^2 for Month 12 and 0.12 mm^2 to 1.44 mm^2 for Month 24 for the difference in the change of GA area from baseline between each pegcetacoplan arm (PM or PEOM) and Sham arm. The precision of the tipping point will be at two decimal points. A tipping point may not exist within reasonable clinical assumptions.

For each analysis, the number and percent of subjects without monotone missing data, the number of subjects with monotone missing data and a breakdown of reasons will be reported. The reasons will include monotone missing without treatment discontinuation or early withdrawal, monotone missing due to treatment discontinuation or early withdrawal due to reasons that are potentially related to study drug or lack of efficacy, and monotone missing due to treatment discontinuation or early withdrawal not due to reasons that are potentially related to study drug or lack of efficacy.

6.2.3.2. Other Sensitivity Analyses

The primary endpoint will also be analyzed without pooling the two sham arms (SM and SEOM). The comparison for pegcetacoplan and sham injection within each dose schedule (i.e., PM vs SM and PEOM vs SEOM, respectively) will be conducted using the MMRM analyses described in Section 6.2.2.

The primary endpoint will also be summarized excluding GA total area assessments with an indeterminate boundary. The summary and presentation of the observed values for the total area of GA lesion(s) by treatment group and visit described in Section 6.2.2 will be repeated. The summary and presentation of the analysis results for all timepoints described in Section 6.2.2 will be repeated.

6.2.4. Supplemental Analyses of the Primary Efficacy Endpoint

6.2.4.1. COVID-19 Adjusted Estimand

Despite the occurrence of the COVID-19 pandemic, the scientific question of interest in this study remains unchanged. The primary scientific research question of this study is to assess the effect of pegcetacoplan compared with that of sham at Month 12 on GA lesion progression under-real life conditions without COVID-19 pandemic impact.

To manage the increase in missed/not received injections due to COVID-19 pandemic (as collected on the eCRF), i.e., undertreatment with an expected relevant impact on efficacy, the hypothetical strategy will be used whereby assessments after the intercurrent event (relevant undertreatment) occurs will be set to missing/censored in the analysis. The threshold for missed/not received injections due to the COVID-19 pandemic is missing a pre-specified number of scheduled injections prior to the analysis timepoint of interest. For the Monthly schedule group, this is missing 2 or more injections and for the EOM schedule group, this is missing 1 or more injections prior to the Month 12 visit attributable due to the COVID-19 pandemic.

In terms of the underlying cause of the excessive missing/not received injections and subsequent missing data, it is assumed that the missingness resulting from censoring occurs at random because of the ongoing pandemic and not because of the subjects' unobserved outcome, so

missing data resulting from this intercurrent event in the primary analysis model will be handled implicitly in the MMRM analysis.

The number of subjects with any censoring included in the model, the number of subjects with any censoring not included in the model, and the number of assessments censored by visit will be presented for each treatment group.

All summaries and presentations of the observed values for the total area of GA lesion(s) in the study eye by treatment group and visit described in Section 6.2.2 will be repeated for the COVID-19 adjusted estimand. All summaries and presentations of the analysis results for all timepoints described in Section 6.2.2 will be repeated for the COVID-19 adjusted estimand. The same plots as for the primary endpoint analysis will be presented.

In addition, a supplemental analysis will also be performed where the threshold for missed/not received injections will be restricted to external events attributable to COVID-19. These events are defined based on the COVID-19 collection form and include COVID-19 diagnosis, COVID-19 Suspected, Site Closure, Travel Ban, Shelter in Place, City Lockdown, and Other. Except for the plots, the analyses described above will be repeated for the threshold based only on these external events attributable to COVID-19.

6.2.4.2. Per Protocol Set

The main analysis described in Section 6.2.2 will be repeated using the Month 12 PP set to investigate the impact of changing the population in the estimand. Any GA lesion area assessments that are deemed not valid according to what is described in Section 4.5 will be set to missing in this analysis. The summary and presentation of the observed values for the total area of GA lesion(s) by treatment group and visit described in Section 6.2.2 will be repeated. The summary and presentation of the analysis results for all timepoints described in Section 6.2.2 will be repeated.

6.2.4.3. Rate of Change Analyses

The mean rate of change in GA area (i.e., slope) will be compared between each pegcetacoplan arm and the pooled sham arm by use of linear mixed effects model assuming time as continuous and linear (“slope model”). The analysis model will include treatment (PM, PEOM, sham), presence of choroidal neovascularization in the fellow eye at baseline (Yes, No), baseline GA lesion area ($< 7.5 \text{ mm}^2$ or $\geq 7.5 \text{ mm}^2$) as fixed effects, time (study month, continuous assuming linearity), the time \times treatment interaction term as well as the baseline GA lesion area \times time interaction term. The response variable will be the GA lesion area. A common unstructured covariance matrix will be used to model the within-subject errors, the sandwich estimator will be used to estimate the standard errors of the fixed effects parameters, and the degrees of freedom will be partitioned into between-subject and within-subject portions. If there are convergence problems with the model, then a heterogeneous autoregressive (1) covariance matrix will be used. If convergence problems still exist, an autoregressive (1) covariance matrix will be used. The mean rate of change (slope), standard error, and confidence interval will be estimated for the baseline to Month 12 as well as the baseline to Month 6 and Month 6 to Month 12 periods for each treatment group. In addition, the estimated difference in slopes among the treatment groups along with the 95% CIs and p-value will be reported. The slopes and 95% CIs will be converted to an annualized rate of growth for each period and each treatment group.

The observed values for the total area of GA lesion(s) will be summarized by treatment group and visit for the baseline to Month 6 and Month 6 to Month 12 time periods. Summaries will present the descriptive statistics for baseline, absolute values and change from baseline to Month 6 and change from Month 6 to Month 12 data. In addition, the annualized rate of growth for each time period will also be presented.

The mean rate of change in GA area will be compared between each pegcetacoplan arm and the pooled sham arm by use of a piecewise linear mixed effect model assuming time as continuous and piecewise linear (“piecewise slope model”). The analysis to be performed will be similar to what is described above in the “slope model” except that a knot at the Month 6 visit will be added which allows for the slope of lesion growth to differ between the two periods for each of the treatment groups. The same presentation as for the “slope model” will be prepared except for the Baseline to Month 12 slope. Additionally, an investigation of the impact of changing the knot to Month 2, 4, 8, 10 will be explored if necessary.

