### **EXTENDED IP ADMINISTRATION WINDOWS**

In order to allow more flexibility to sites and subjects, and to potentially mitigate missed IP administration, an extended IP administration window can be followed. The extended window can ONLY be used in situations related to COVID-19 restrictions and after medical monitor approval. Footnote “T” of each COVID-19 assessment table below reflects these extended IP options.

Per protocol, the IP administration window is as follows:

- Monthly treatment group: +/- 8 days for the entire study duration
- EOM treatment group: +/- 8 days for the first study year and +/- 16 days for the second study year

During COVID-19 restrictions, the IP administration window can be extended to the following:

- Monthly treatment group: -8 days to +15 days. Note, interval for consecutive injections must be at least 14 days.
- EOM treatment group: -8 days to +30 days for the first study year and -16 days to +30 days for the second study year.

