3.6. Definition of 12-Month Data in the Month 12 Dataset

All screening and post-baseline data with a clinical date (i.e., administration/assessment/onset/start date) on or before the defined Month 12 data cutoff date will be included in the Month 12 Dataset. The 12-month data cutoff will include all data regardless of the type of study visit at which it was collected. This may include data collected at unscheduled visits or early termination visits if the visit date was on or before the 12-month data cutoff date. The Month 12 data cutoff is defined as:

- If the subject completed Month 12 (Visit 14) assessments, then the data cutoff will be the day that the Month 12 (Visit 14) assessments are completed, regardless of Study Day.
- If the subject did not complete the Month 12 (Visit 14) assessments (e.g. missed or early terminated) then Study Day 375 (Study Day 360 (target date) + 15) will be used as the Month 12 cutoff.

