13.3. Definition of Relative Study Days

Unless otherwise noted, relative study days (Rel Days) of an evaluation are defined as number of days relative to the first dose date of study drug which is designated as Day 1, and the preceding day is Day -1, the day before that is Day -2, etc.

If evaluation date is on or after first dose date, then relative study days are calculated as

$$\text{Evaluation date} - \text{first dose date of study drug} + 1.$$

If evaluation date is before first dose date, then relative study days are calculated as

$$\text{Evaluation date} - \text{first dose date of study drug}$$

Relative study days take negative values if evaluation date occurs prior to first dose date and take positive values if evaluation date occurs on or after first dose date of study drug.

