13.4. Definition of Visit Windows

All assessments occurring on or before the first date of dosing (Analysis Study Day (ADY) ≤ 1) will be assigned to the Baseline analysis visit window.

Unless otherwise specified, the actual scheduled nominal post-baseline visit will be used for over time summaries. Post-baseline unscheduled visits and early termination visits will be mapped to a scheduled visit and will only be used in the analysis if the nominal scheduled visit result is missing, [Table 5](#) and [Table 6](#) presents the analysis visit window mapping for unscheduled and early term visits. In the case that multiple unscheduled or early termination visits are in the same analysis window, the one closest to the target date will be used. In the event that windowed visit is mapped to an illogical sequence of visits when considering nearby scheduled visits

(i.e., windowed visit is higher than the subsequent visit or lower than the preceding visit), the windowed visit will be set to the logical scheduled visit.

Table 5: Post-Baseline Analysis Visit Window for Unscheduled and Early Termination Visits: Monthly Regimen

Analysis Visit	Target Study Day	Analysis Window (days)
Day 7	7	2 to 15
Month 1	30	16 to 45
Month 2	60	46 to 75
Month 3	90	76 to 105
Month 4	120	106 to 135
Month 5	150	136 to 165
Month 6	180	166 to 195
Month 7	210	196 to 225
Month 8	240	226 to 255
Month 9	270	256 to 285
Month 10	300	286 to 315
Month 11	330	316 to 345
Month 12	360	346 to 375
Month 13	390	376 to 405
Month 14	420	406 to 435
Month 15	450	436 to 465
Month 16	480	466 to 495
Month 17	510	496 to 525
Month 18	540	526 to 555
Month 19	570	556 to 585
Month 20	600	586 to 615
Month 21	630	616 to 645
Month 22	660	646 to 675
Month 23	690	676 to 705
Month 24	720	706 to EOS

Table 6: Post-Baseline Analysis Visit Window for Unscheduled and Early Termination Visits: Every Other Month Regimen

Analysis Visit	Target Study Day	Analysis Window (days)
Day 7	7	2 to 15
Month 1	30	16 to 45
Month 2	60	46 to 75
Month 3	90	76 to 105
Month 4	120	106 to 135
Month 5	150	136 to 165
Month 6	180	166 to 195
Month 7	210	196 to 225
Month 8	240	226 to 255
Month 9	270	256 to 285
Month 10	300	286 to 315
Month 11	330	316 to 345
Month 12	360	346 to 375
Month 14	420	376 to 450
Month 16	480	451 to 510
Month 18	540	511 to 570
Month 20	600	571 to 630
Month 22	660	631 to 690
Month 24	720	690 to EOS

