1.2 Sample of SAS Code

- * The SAS codes in this section are shown as examples
- * Some modifications (such as variables used in the model statement)
- * may require further changes to reflect the methods specified in the
- * SAP and analysis data structure
- * e.g., change trtan to trtpn to reflect analysis w/ the ITT set;

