1.2.3. Rate of Change Models

```
*****;
*** Rate of Change analyses ***;

* In this example, repeated measures are available at
* avisitn = 0 (baseline), 2 (Month 2), 4 (Month 4)
* 6 (Month 6), 8 (Month 8), 10 (Month 10) and 12 (Month 12)
*
* AVAL is the actual GA lesion measurement at the corresponding visit * for
the study eye from ADGA.
* SGALESAT is the GA lesion size (categorical) at baseline
* FCNVAT is the fellow eye CNV status at baseline
* TR01PG2N is the pooled treatment group (1 = PM, 2 = PEOM, 3 = Sham)
* T is equivalent to AVISITN
*
* The data is read in from ADGA
*****;

proc mixed data=ga method=reml covtest empirical;
```

```
class subjid TR01PG2N FCNVAT SGALESAT t;
model aval = SGALESAT TR01PG2N avisitn TR01PG2N * avisitn
          SGALESAT*avisitn FCNVAT/cl solution;
repeated t /type=un sub=subjid r ;

**Month 6;
estimate 'PM Month 0 to 6 slope' TR01PG2N*avisitn 6 0 0
          avisitn 6 SGALESAT*avisitn 3 3 /cl;
estimate 'PEOM Month 0 to 6 slope' TR01PG2N*avisitn 0 6 0
          avisitn 6 SGALESAT*avisitn 3 3 /cl;
estimate 'Sham Month 0 to 6 slope' TR01PG2N*avisitn 0 0 6
          avisitn 6 SGALESAT*avisitn 3 3 /cl;

estimate 'Month 0 to Month 6 Difference in slope PM - Sham'
          TR01PG2N*avisitn 6 0 -6 /cl;
estimate 'Month 0 to Month 6 Difference in slope PEOM - Sham'
          TR01PG2N*avisitn 0 6 -6 /cl;
estimate 'Month 0 to Month 6 Difference in slope PM - PEOM'
          TR01PG2N*avisitn 6 -6 0 /cl;

**Month 12;
estimate 'PM Month 6 to 12 slope' TR01PG2N*avisitn 6 0 0
          avisitn 6 SGALESAT*avisitn 3 3 /cl;
estimate 'PEOM Month 6 to 12 slope' TR01PG2N*avisitn 0 6 0
          avisitn 6 SGALESAT*avisitn 3 3 /cl;
estimate 'Sham Month 6 to 12 slope' TR01PG2N*avisitn 0 0 6
          avisitn 6 SGALESAT*avisitn 3 3 /cl;

estimate 'Month 6 to 12 Difference in slope PM - Sham'
          TR01PG2N*avisitn 6 0 -6 /cl;
estimate 'Month 6 to 12 Difference in slope PEOM - Sham'
          TR01PG2N*avisitn 0 6 -6 /cl;
estimate 'Month 6 to 12 Difference in slope PM - PEOM'
          TR01PG2N*avisitn 6 -6 0 /cl;

ods output diffs= diff2 LSMeans= LSMean2 CovParms = COV2
          estimates = estimates2;

**Month 0 to 12;
estimate 'PM Month 0 to 12 slope' TR01PG2N*avisitn 12 0 0
          avisitn 12 SGALESAT*avisitn 6 6 /cl;
estimate 'PEOM Month 0 to 12 slope' TR01PG2N*avisitn 0 12 0
          avisitn 12 SGALESAT*avisitn 6 6 /cl;
estimate 'Sham Month 0 to 12 slope' TR01PG2N*avisitn 0 0 12
          avisitn 12 SGALESAT*avisitn 6 6 /cl;

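### The supplemental growth-rate models use nominal visit month as continuous time although image dates are available; actual elapsed time would be a free refinement

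*SAP*

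**What the plan says.** SAP 6.2.4.3 models lesion area with time entered as "time (study month, continuous assuming linearity". It reports slopes for baseline to Month 12, baseline to Month 6 and Month 6 to Month 12, with differences between arms, confidence intervals, p-values and annualised rates. In the piecewise version "a knot at the Month 6 visit will be added". SAP 6.2.6 carries both models to 24 months.

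The sample code in SAP Appendix 1.2.3 shows what study month means. AVISITN takes the values 0, 2, 4, ... 12 and is the continuous regressor, and a comment records that "T is equivalent to AVISITN". SAP 13.4 sets the same convention: "the actual scheduled nominal post-baseline visit will be used for over time summaries". Unscheduled and early-termination results are mapped to a nominal visit when that visit's own result is missing.

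Actual timing is held. In SAP 13.3, "relative study days (Rel Days) of an evaluation are defined as number of days relative to the first dose date of study drug". SAP 3.6 builds the Month 12 cutoff on a clinical date ("i.e., administration/assessment/onset/start date") and keeps a completed Month 12 visit whatever its study day.

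The Protocol visit schedules (Appendices A to D) allow +/-8 days in year 1 for both regimens. In year 2 they allow +/-8 days (monthly) and +/-16 days (EOM). Appendix K adds: "During COVID-19 restrictions, the IP administration window can be extended to the following", namely -8 to +15 days (monthly), and -8 to +30 days in year 1 or -16 to +30 days in year 2 (EOM).

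**The concern.** A slope is area per unit of time, so an error in the time axis goes into the estimate. An image taken late carries extra growth that nominal month attributes to the scheduled interval.

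If deviations average zero in each regimen, the result is only noise. If one regimen runs later on average, the error does not cancel, because the sham group pools about 100 monthly and 100 EOM subjects. Late EOM visits add a full delay's growth to PEOM, half a delay's growth on average to sham, and none to PM. The two contrasts then move in opposite directions: PM looks better against sham and PEOM looks worse. At stake are the supplemental slope estimates and their p-values.

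**Working it through.** **Inputs.** Planned growth is 1.47 (PM), 1.70 (PEOM) and 2.13 (sham) mm2/year, SD 1.50 mm2, 200 per group (SAP 3.4). The planned differences from sham are 0.66 and 0.43. Sham is half monthly and half EOM (Protocol Table 1). Actual deviations are not in the documents, so the delay is an assumption: EOM visits later than monthly visits by 1 to 5 days on average.

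**Plan's own figure.** The documents give no figure for the slope models, so the check is on the growth inputs through the power table. The standard error is 1.5 x sqrt(2/200) = 0.15, and the critical value at two-sided 0.0495 is 1.964.
- PM: 0.66/0.15 - 1.964 = 2.436, power 99.3% (stated 99.2%).
- PEOM: 0.43/0.15 - 1.964 = 0.903, power 81.7% (stated 81.5%).

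The inputs reproduce.

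**Noise when deviations average zero.** Sham growth is 2.13/365.25 = 0.00583 mm2/day.
- Uniform scatter over +/-8 days: SD 8/sqrt(3) = 4.6 days, or 0.027 mm2. Relative to the growth variance, 0.027^2/1.5^2 = 0.03%.
- Uniform scatter over +/-16 days: SD 9.2 days, or 0.054 mm2, which is 0.13% of that variance.

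**Shift in the Month 12 area difference, per day of mean EOM delay.**
- PEOM minus sham: (1.70 - 2.13/2)/365.25 = 0.635/365.25 = +0.00174 mm2. For 1 to 5 days: +0.002 to +0.009 mm2. The upper value is 0.0087/0.43 = 2.0%.
- PM minus sham: -(2.13/2)/365.25 = -1.065/365.25 = -0.00292 mm2. For 1 to 5 days: -0.003 to -0.015 mm2. The upper value is 0.0146/0.66 = 2.2%.

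**Shift in the fitted 12-month slope.** Assume images at months 0, 2, ... 12, an on-time baseline, and a random intercept and slope with independent error. Generalised least squares then reduces to ordinary least squares. Mean time is 6 and the sum of squares about it is 112. A constant delay of d days at the six post-baseline visits raises the slope by the fraction (d/30) x 6/112 = 0.00179d.
- PEOM minus sham: 0.635 x 0.00179 = +0.0011 mm2/year per day, so +0.001 to +0.006 for 1 to 5 days.
- PM minus sham: -1.065 x 0.00179 = -0.0019 per day, so -0.002 to -0.010.

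At a uniform 30-day delay the same formula moves PEOM minus sham from -0.43 to -0.396 and PM minus sham from -0.66 to -0.717.

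**Fitted 24-month slope, delay in year 2 only.** For months 0, 2, ... 24 the sum of squares about 12 is 728, and the year-2 visits contribute 2+4+6+8+10+12 = 42. The fraction is (d/30) x 42/728 = 0.00192d. For 1 to 5 days this gives +0.001 to +0.006 mm2/year (PEOM) and -0.002 to -0.010 (PM).

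**The case against.** The other side has good arguments. These analyses are supplemental and sit outside the tested hierarchy. Nominal month keeps the slopes on the same visit scale as the primary MMRM. The code is flagged as illustrative: "The SAS codes in this section are shown as examples". Mapped unscheduled visits enter only when the nominal result is missing. Under the assumed delays the effect is about 2% or less. All of this stands, and it limits the weight of the point. It does not supply a reason to prefer nominal time: code and SAP 13.4 agree on it, and neither 6.2.4.3 nor 6.2.6 offers a version on actual dates.

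A reader might infer more than the documents support:
- **That year-1 imaging windows differ by regimen.** The +15 and +30 day limits apply to administration of study product and need medical monitor approval. The COVID schedules still show +/-8 days for year-1 visits, and dosing may fall on a different day from assessment. EOM FAF visits in year 1 are all dosing visits, so images could have moved with the dose, but no text says that they did. The scheduled-visit difference that is documented is the year-2 one.
- **That a 30-day delay costs 41% of the effect.** One eye at the sham rate would carry 30 x 0.00583 = 0.17 mm2, and 0.17/0.43 is about 41%. This compares a single eye at the edge of a dosing window with a difference in group means; a PEOM eye would carry 0.14.
- **That the bias reaches 15% to 18%.** That needs every monthly visit 8 days early and every EOM visit 30 days late.
- **That annualised rates are 1.4% low.** This follows from 360/365.25 only if monthly slopes are multiplied by 12. The SAP states no factor, and a common factor would leave percentage reductions and p-values unchanged.

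**Conclusion.** The point holds as a minor one. Both slope models use nominal month as continuous time while the dates needed for an exact time axis are available. Under an assumed mean EOM delay of 1 to 5 days, the Month 12 area difference shifts by about +0.002 to +0.009 mm2 for PEOM minus sham and -0.003 to -0.015 mm2 for PM minus sham, with somewhat smaller shifts in the fitted slopes. With no difference in mean delay there is no bias. The size rests on the planned growth rates, linear growth, an even sham split and the assumed delay; the slope figures also rest on the simple covariance structure used above. The primary MMRM treats time as categorical, and neither it nor type I error is affected. Severity: nice to have.

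**What to change.** In the linear and piecewise slope models, replace AVISITN as the continuous regressor by (FAF image date minus baseline FAF image date)/30.4375. Derive the knot variable from the same quantity. Keep nominal visit (T) only in the REPEATED statement, where it indexes the unstructured covariance. State that rates are annualised per 365.25 days; with time in these units, the existing 12-month ESTIMATE coefficients give that directly. Add a table of actual minus target day by arm and visit, so that any regimen difference in timing can be seen.

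The cost is one derived variable, a small code change and one table. No new data are needed. Under the models' own assumption of linear (or piecewise linear) growth, this removes the timing error.

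### SAP 6.2.4.3 asks a model with one slope per arm for separate Month 0–6 and Month 6–12 slopes; those rows can only repeat the full-year slope

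*SAP*

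**What the plan says.** SAP Section 6.2.4.3 describes two models for the rate of change in GA area.

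- **Slope model.** This is a "linear mixed effects model assuming time as continuous and linear". Its time terms are time, time by treatment, and baseline lesion-size category by time. The mean slope, its confidence interval and its standard error "will be estimated for the baseline to Month 12 as well as the baseline to Month 6 and Month 6 to Month 12 periods" in each treatment group. Arm differences in slope, with intervals and a p-value, are also requested, without naming a period. Then: "The slopes and 95% CIs will be converted to an annualized rate of growth for each period and each treatment group".
- **Piecewise slope model.** This adds a knot at Month 6, "which allows for the slope of lesion growth to differ between the two periods for each of the treatment groups". It takes over the slope model's presentation, which "will be prepared except for the Baseline to Month 12 slope".

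The same section also plans observed-value summaries and annualised rates for the two half-years.

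SAP Appendix Section 1.2.3 gives code for both models, under the general note that "The SAS codes in this section are shown as examples". In the linear model the statements begin "estimate 'PM Month 0 to 6 slope' TR01PG2N*avisitn 6 0 0" and "estimate 'PM Month 6 to 12 slope' TR01PG2N*avisitn 6 0 0". SAP Section 6.2.6 repeats the Section 6.2.4 analyses for the full 24 months and does not define slope periods for that repeat.

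**The concern.** A model that is linear in time has one slope per arm, and nothing in it lets the slope change at Month 6. Asking it for a Month 0–6 slope and a Month 6–12 slope returns the same quantity under two labels.

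What is at stake is interpretation. A row labelled Month 6 to 12, with a treatment difference and a small p-value, invites the reading that the effect was maintained in the second half-year. The linear model cannot show that, because the row is the full-year slope rescaled. The piecewise model produces rows for the same half-years, and in the example code they carry the same labels. A reader could then find two different answers under one label.

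**Working it through.** **1. Algebra of the slope model.** For a given arm, averaged equally over the two lesion-size categories as in the code, let s be the monthly slope: the time coefficient, plus the arm's time-by-treatment coefficient, plus the mean of the two category-by-time coefficients. Model-based growth from month u to month v is (v − u) × s.

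| Period | Growth | Annualising factor | Annualised rate |
|---|---|---|---|
| Month 0–6 | 6s | 2 | 12s |
| Month 6–12 | 6s | 2 | 12s |
| Month 0–12 | 12s | 1 | 12s |

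The standard error scales by the same constants, so t = s / SE(s) and its p-value are the same in all three rows. This holds for any data. The category-by-time term gives each lesion-size category its own slope, but that slope is also constant over time.

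**2. The example code (SAP Appendix Section 1.2.3).** Time is not in the CLASS statement, so it is continuous. There is one PROC MIXED fit and no refit by period.

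| Linear-model contrast | Month 0–6 | Month 6–12 | Month 0–12 |
|---|---|---|---|
| PM slope: treatment-by-time | 6 0 0 | 6 0 0 | 12 0 0 |
| PM slope: time | 6 | 6 | 12 |
| PM slope: category-by-time | 3 3 | 3 3 | 6 6 |
| PM − Sham | 6 0 −6 | 6 0 −6 | 12 0 −12 |

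The other arms and differences follow the same pattern. Each period has 3 arm slopes and 3 differences, so there are 3 × 6 = 18 statements. They hold 6 distinct contrasts up to scale. As coded, the raw output has 12 distinct estimates (6 half-year and 6 full-year). The reduction to 6 appears once results are annualised, and in t and p at once. The 3 periods × 3 arms = 9 annualised rates required by the text take 3 values.

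**3. When the repetition matters.** If growth is linear, the piecewise model's two slopes have the same expectation as the single slope. If growth bends in the same way in every arm, arm slopes can be wrong for a half-year, but with complete data the shared bend cancels from the arm differences. Only a bend that differs by arm can distort the half-year differences.

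**4. Illustration, hypothetical.** Inputs from SAP Section 3.4: means of 1.47 (PM) and 2.13 (sham) mm²/year, SD 1.50 mm², 200 per arm. The 12-month difference is 1.47 − 2.13 = −0.66 mm². Assumptions not in the documents:

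- a split of that difference of 0.60 mm² in Months 0–6 and 0.06 mm² in Months 6–12;
- FAF complete at Months 0, 2, …, 12;
- covariance symmetric in time (random walk, random slope, or an equal mix);
- measurement-error SD 0.1 to 0.5 mm² and baseline SD 4 mm².

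Generalised least squares on the PM − sham mean difference gives:

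- *Linear model.* Both half-years are estimated at −(0.60 + 0.06)/2 = −0.33 mm². With little measurement error the SE is about ½ × 1.50 × √(2/200) = 0.075; over the error range it is 0.072 to 0.075. So z is 0.33/0.075 = 4.4 or more, and p is about 0.00001 or smaller.
- *Piecewise model, Month 6–12.* The estimate is −0.06 mm² with SE 0.076 to 0.114, so p is 0.43 to 0.60.

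Under these conditions each linear half-year row is off by half the gap between the two half-year differences: (0.60 − 0.06)/2 = 0.27 mm² here. A milder split of 0.40/0.26 gives (0.40 − 0.26)/2 = 0.07 mm². An even split of 0.33/0.33 gives zero, and both models then return −0.33 mm² for each half-year. With dropout or a covariance that is not symmetric in time the −0.33 moves, but the two linear half-year rows still equal each other.

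**The case against.** The case for leaving the text alone has several parts.

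- **Low consequence.** The analysis is supplemental and outside the testing procedures in SAP Sections 6.2.1 and 6.3.1. The piecewise model and the observed half-year summaries already give valid period results. This stands, and it keeps the point minor.
- **The rows are not empty.** A reader might infer that they hold no information, or that they always misstate both half-years. Neither follows. Under the model's own linearity assumption the common slope is a valid estimate for each half-year, and a bend shared by all arms leaves the arm differences intact. What stands is narrower: the rows cannot show a difference between periods.
- **The models are named separately.** Two named models may properly give different estimates. The identical row labels, and the half-year arm differences from the linear model, appear only in code marked as examples. That is fair, but the half-year slopes and annualised rates are required by the text itself.
- **A refit by period may be meant.** Fitting the slope model to each half-year's visits would give separate slopes. The documents do not support this reading: Section 6.2.4.3 describes one model, presents the knot as what lets the slopes differ, and the code has a single fit.
- **The illustration is chosen.** The 0.60/0.06 split has no basis in the documents and alone creates the conflict. It shows what could happen, not what to expect.

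**Conclusion.** The point holds as a minor inconsistency. Section 6.2.4.3 requests half-year slopes, intervals and annualised rates from a model that has one slope per arm, so following the text prints the full-year result under half-year labels. That part is algebra and needs no assumption: 18 statements with 6 contrasts up to scale, and 9 annualised rates with 3 values. Whether those rows would also be wrong depends on growth being non-linear, and for arm differences on the non-linearity differing by arm. The documents give no figure for either, so the conflict in the illustration is conditional and disappears under an even split.

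A reader might take this as a weakness in the evidence for efficacy. The documents do not support that: the primary analysis is the MMRM of SAP Section 6.2.2, with time categorical, and no tested hypothesis uses these rows.

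**What to change.** In SAP Section 6.2.4.3, limit the linear slope model to the baseline-to-Month-12 slope, its annualised rate and its arm differences. State that all Month 0–6 and Month 6–12 slopes, annualised rates, differences, intervals and p-values come from the piecewise model. Delete the 12 half-year ESTIMATE statements from the linear-model example code in Appendix Section 1.2.3. Apply the same rule to any 24-month repeat under Section 6.2.6.

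The cost is one wording change and the deletion of 12 example statements (24 code lines). No valid planned result is lost, because every half-year slope and difference is already planned from the piecewise model. The change also mirrors the SAP's own choice to leave the full-year slope out of the piecewise presentation.
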